- Global opinion on the effect of investigational treatment will be reported by patient if able to express himself. If not will be reported either by parents or teachers.
- Investigational treatment allocation: start 1-week wash-out period.

T1 - Telephone contact at D59 (± 1 day)

During this telephone contact, the investigator should:

- Ascertain that the treatment discontinuation is well tolerated
- Record all adverse events that have occurred
- Withdrawal symptoms questionnaire

V8 - End of study visit after 1 week of placebo wash out or (D63 \pm 2 days) / Start of Open label or Premature withdrawal visit (within 5 days after last treatment intake)

The premature withdrawal patients should be followed by a visit performed within a maximum of 5 days after the last dose of study drug.

- A complete interrogation including control of the treatment compliance, count of remaining tablets and verification of the forgotten treatment intake.
- Adverse events and concomitant medication recording,
- A physical examination including vital signs shall be carried out,
- 12-lead ECG (QTcF value),
- A blood sample will be taken for routine haematological and biochemical test (including β -HCG pregnancy test for pubescent female) and semi-quantitative urinalysis (dipstick). (only for premature withdrawal patients),
- The following questionnaires should be performed:
 - PDSS.
 - CASS.
 - UNS (only for premature withdrawal patients),
 - CGI-C on EDS and on cataplexy,
 - CDI,
 - C-SSRS.
 - -Global opinion on the effect of investigational treatment will be reported by patient if able to express himself. If not will be reported either by parents or teachers. (only for premature withdrawal patients),
 - Retrieval of sleep diary.
 - -Withdrawal symptoms questionnaires.

Patients willing to continue the study in the prolonged open label period will receive a new pack of investigational treatment and will start an escalating dose treatment. Those patients will receive one sleep diary which have to be filled out daily during the 7 days prior to the next visit. Patients not willing to continue in the study will be followed under usual practice.

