5. CONDUCT OF THE STUDY

5.1. **EXPECTED DURATION OF SUBJECT PARTICIPATION**

The expected duration of patient participation from the screening visit (V0) until the final visit

Confidential 71

BIOPROJET Version 3.0 Protocol P11-06/ BF2.649 September 30th, 2020

EudraCT number: 2013-001506-29 (V8) will be 13 weeks:

Baseline period without investigational treatments (from V0 to V2): 4 weeks.

• Low and medium dose titration phase (from V2 to V3): 2 weeks

• Individual dose adjustments (from V3 to V5): 2 weeks

• Stable dose phase (from V5 to V7): 4 weeks

• 1-week study drug wash out (placebo) after study drug discontinuation

During the double blind phase, the patient will be followed in an ambulatory way by 9 visits on the site.

The double blind phase will be followed by a prolonged open-label period if patient wishes, until BF2.649 (pitolisant) is available on the marketfor children/adolescent from 6 to 17 years included or as soon as the patient becomes older than 18 years. Then, he will have access to the treatment already on the market for adults.

The first inclusion of this study is scheduled in Q1 2016. The end of the double-blind phase is expected by Q1 2022.

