5.2.16. V13- Dose adjustment visit (Day 364± 7 days)

Idem to the visit V12.

A blood sample will be taken for routine haematological and biochemical test (including β-

HCG pregnancy test for pubescent female) and semi-quantitative urinalysis (dipstick),

Dose allocation: either 5, 10, 15, 20, 30 or 40 mg/day or placebo in the morning during 6-month.

Patients with a weight less than 40 kg could be treated with a maximum daily dose up to 20 mg.

All subsequent visits are performed each 6 months as V13.

The investigator should instruct each patient to report any subsequent event(s) that the patient

or his personal physician believes might reasonably be related to participation of this study.

In case of occurrence of adverse event or in case of unresolved adverse event, the investigator

should schedule an additional follow-up in order to follow any adverse events until they are

resolved. Thereafter, the patient will be discharged from the study.

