5.2.17. Early withdrawal visit (Open label phase)

The premature withdrawal patients from the study should be followed by a visit performed

within a maximum of 5 days after the last dose of study drug.

Tests and exams are applied as V13 with no dispensation.

Patients will be followed under usual practice after their study discontinuation.

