5.3.2. Type and timing of data to be collected from withdrawn patients

When a patient is prematurely withdrawn from the study before the "End of study visit" V8, the investigator has to perform a complete visit, within a maximum of 5 days after the last dose of study drug. This will also apply for open label phase.

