6.1.5.1. Definitions

Period of observation

For the purpose of this study, the period of observation extends from the time the patient gives

informed consent (Visit 0) until one month after the last drug administration and until resolution

of ongoing drug related adverse event. Any adverse events observed by the investigator or

reported by the patient during the period of observation must be documented in the CRF.

Adverse event

The term **Adverse Event** covers any sign, symptom, syndrome, or illness which appears or

BIOPROJET Version 3.0
Protocol P11-06/ BF2.649 September 30th, 2020

EudraCT number: 2013-001506-29

worsens in a patient during the observation period in the clinical study, and which may impair

the patient's well-being.

The term also covers laboratory findings or results of other diagnostic procedures which are

considered to be clinically relevant (e.g., requiring unscheduled diagnostic procedures or

treatment measures, or result in withdrawal from the study).

An adverse event may be:

A new illness:

The worsening of a sign or symptom of the condition under treatment, or of a concomitant

illness;

An effect of the study medication;

A combination of two or more of these factors.

No causal relationship with the study medication or with the clinical study itself is implied by

the use of the term "Adverse Event."

• Exemption conditions

In this study in narcoleptic patients, symptoms like hallucinations, sleep attacks and sudden

onset of sleep should be considered as symptoms of the underlying condition and not as adverse

event, and should only be reported as Adverse Event in case of worsening or unusual form.

• Treatment-Emergent Adverse Event (TEAE)

A treatment-emergent adverse event is defined as any event not present prior to the initiation

of the study treatments, or any event already present which worsens either in intensity, or

frequency following the exposure to the study treatment.

• Adverse Drug Reaction (ADR)

All noxious and unintended responses to a medicinal product related to any dose should be

considered as an Adverse Drug Reaction. The responses to a medicinal product means that a

causal relationship between a medicinal product and an Adverse Event is at least a reasonable

possibility, i.e. the relationship cannot be ruled out. The causal relationship should be assessed

as defined below §7.2.5.3 (assessment of causality).

• Unexpected Adverse Drug Reaction

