## • Treatment Emergent Adverse Event

A Treatment Emergent Adverse Event (TEAE) corresponds to an Adverse Event (AE) that occurred on or after first dose of treatment up to 7 days post-last dose.

In case of partially/fully missing AE start date:

- Following imputation rules should be applied in order to determine whether the AE is treatment-emergent or not:
  - If only start day is missing, then it will be replaced by the minimum of (last day of the month, last treatment dose intake)
  - If both start day and month are missing then:
    - if year is equal to the year of the first treatment dose intake, then start date will be replaced by the first treatment dose intake

- if year is greater than the year of the first treatment dose intake and equal to the year of the last treatment dose intake, then start date will be replaced by the last treatment dose intake
- if year is greater than the year of the first treatment dose intake and smaller than the year of the last treatment dose intake, then start date will be replaced by 1-July
- $\circ~$  If start date if fully missing, then start date will be replaced by the date of the first treatment dose intake
- Emergence will be checked in accordance with the response to the question « Started before study drug intake ». If the response is "Yes" the AE can't be considered as emergent

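### Adverse events are to be observed for one month after the last dose, but the last scheduled enquiry for a child who stops is at 5 days or less (withdrawn) or nominally 7 days (completer), and the SAP counts to 7 days

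*Protocol*

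**What the plan says.** **Observation period.** Protocol 6.1.5.1 sets the period from "informed consent (Visit 0) until one month after the last drug administration and until resolution" of any drug-related event still ongoing. Events that the investigator observes or the patient reports in that time must go into the CRF. Section 6.1.5.2 says how events come to light: by spontaneous report or at interview. It has the investigator put one standard opening question to each patient, for uniformity.

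**Withdrawn children.** Under Protocol 5.3.2, "the investigator has to perform a complete visit, within a maximum of 5 days after the last dose of study drug". The same section extends this to the open-label phase, and 5.2.10 and 5.2.17 repeat it. After open-label withdrawal, "Patients will be followed under usual practice after their study discontinuation". Section 5.3.3 adds a follow-up visit if an event has not resolved at withdrawal, and asks for efforts to reach a child who fails to attend.

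**Completers who do not continue.** Section 5.1 gives a "1-week study drug wash out (placebo) after study drug discontinuation". The Synopsis describes V8 as "End of study visit after 1 week of placebo wash out", at D63 ± 2, after V7 at D56 ± 2, with a call (T1) at D59 ± 1. Those who decline open label then return to usual practice (Synopsis and 5.2.10).

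**Later reporting.** Section 5.2.16, which describes open-label visit V13, asks the investigator to instruct patients to report later events that the patient "or his personal physician believes might reasonably be related to participation of this study".

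**Analysis.** SAP 4.1.5.6 defines a treatment-emergent event as one that "occurred on or after first dose of treatment up to 7 days post-last dose", and a non-treatment-emergent event as one before treatment. SAP 4.5.4.1 tabulates events over V2–V8.

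**The concern.** The stated observation period is several times longer than the time in which anyone is scheduled to ask. Neither the double-blind nor the open-label schedule table has a contact near one month after the last dose. A study report that repeats section 6.1.5.1 would describe a one-month post-treatment safety follow-up in children that the schedule does not actively support.

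Two consequences bear on the safety data:

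- Within the SAP's own 7-day window, the time asked about differs between children who complete and children who withdraw. Withdrawal may be influenced by treatment, so the comparison of event rates rests partly on unequal ascertainment.
- A new event arising after day 7 in a child who stops has no clear place in the SAP. It is not treatment-emergent, it is not non-treatment-emergent, and after V8 it lies outside the tabulated period. Even if reported, it could be missing from the tables.

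**Working it through.** No power or alpha figure is involved. The check is day arithmetic on the schedule.

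**Inputs**
- V7 at D56 ± 2 and V8 at D63 ± 2 (double-blind schedule table).
- Withdrawal visit at most 5 days after the last dose (Protocol 5.3.2, 5.2.17).
- Treatment-emergent window: 7 days after the last dose (SAP 4.1.5.6).
- One month: the protocol gives no number of days. Assumed 30, range 28–31.

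**The plan's own figure.** V8 − V7 = 63 − 56 = 7 days, which matches the stated one-week wash-out. With both visit windows the gap runs from (63 − 2) − (56 + 2) = 3 days to (63 + 2) − (56 − 2) = 11 days.

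**Share of the month with no scheduled enquiry** = (days in month − day of last scheduled contact) / days in month.

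| Child | Last contact | 28 days | 30 days | 31 days |
|---|---|---|---|---|
| Withdrawn, seen at the limit | day 5 | 23/28 = 82% | 25/30 = 83% | 26/31 = 84% |
| Completer who stops, nominal V8 | day 7 | 21/28 = 75% | 23/30 = 77% | 24/31 = 77% |

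At nominal timing the range is therefore 75–84%. A withdrawn child seen before day 5 has a larger share.

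**Sensitivity for completers**
- With the visit windows and a 30-day month: (30 − 11)/30 = 63% to (30 − 3)/30 = 90%. The lowest value over 28–31 days is 17/28 = 61%.
- The figures above count from the last double-blind dose. SAP 4.1.5.2 also takes last intake from V2–V7. If the protocol's last drug administration means the last wash-out placebo tablet, V8 falls about 0–1 day after it. The share is then 29/30 = 97% to 100% for a 30-day month.

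In every variant more than half the month is unsolicited.

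**Against the 7-day window.** For a withdrawn child, 7 − 5 = 2 days, so at least the last 2 days have no scheduled enquiry. For a completer at nominal timing, T1 and V8 cover all 7 days. If V8 comes only 3 days after V7, 7 − 3 = 4 days are not covered, so full coverage of completers is nominal and not guaranteed.

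**The case against.** The strongest reply is that section 6.1.5.1 creates a duty to record, not a promise to ask. It covers events observed or reported, and 6.1.5.2 accepts spontaneous reports. That is correct, and a reader should not infer that the protocol commits to a visit at one month. But 6.1.5.2 also makes a uniform question to each patient part of the method, and spontaneous reporting does not give uniform ascertainment.

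It is also tempting to say that most of the month is never asked about. The documents do not support that. Section 9.1 keeps the investigator available by telephone. Sections 5.3.3, 6.1.5.2 and 6.1.5.3 follow unresolved events past the last visit, and 5.3.3 pursues non-attenders. These routes are passive or triggered by a known event or a missed visit; none is a scheduled enquiry about new events. For the same reason the 2-day shortfall does not apply to every withdrawn child, since one with an unresolved event should have further contact.

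Nor does 5.2.16 tell patients to report related events only. It asks for events believed related and is silent on others. It is still narrower than 6.1.5.1, and its place under V13 leaves unclear whether it reaches children who stop in the double-blind phase.

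Finally, events on days 8–30 cannot change the planned treatment-emergent comparison, because the SAP does not count them. This is true. The direct effect on that comparison is limited to the end of the 7-day window. The remainder is a mismatch between the stated follow-up and what is collected and tabulated.

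**Conclusion.** The mismatch is real. About 75–84% of the stated month has no scheduled enquiry for a child who stops, and 61% or more under every reading of the windows and of one month. A withdrawn child without an unresolved event also has no scheduled enquiry for at least the last 2 days of the SAP's 7-day window.

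This rests on a 28–31 day month and, for completers, on counting from the last double-blind dose. Children who enter open label are not affected at V8. The gap reappears if they later withdraw, although this SAP covers the blinded part only.

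A reader might infer that late events are under-counted mainly on pitolisant. The documents do not support that: they give no withdrawal numbers or split by arm, and a child who leaves with an unresolved event is the one for whom 5.3.3 provides extra follow-up. What can be said is that ascertainment depends on withdrawal status, with the direction by arm and the number of children unknown.

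**What to change.** Reconcile the Synopsis (V8 entry) and Protocol 5.2.10, 5.2.16, 5.2.17, 5.3.2 and 6.1.5.1 with SAP 4.1.5.6 and 4.5.4.1. There are two consistent ways to do this:

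1. Keep the stated period. Add one telephone adverse event enquiry in the T1 format at its end for each child who withdraws or does not continue. State in the SAP how events after the treatment-emergent window are classified and tabulated.
2. Restate the period as what the schedule covers, align the withdrawal contact with the treatment-emergent window, and report the length of post-dose follow-up by arm. Restating the period alone would leave the 5-day visit short of the 7-day window.

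Under either route, say which dose counts as the last drug administration, and make the reporting instruction in 5.2.16 consistent with 6.1.5.1 in the events and children it covers.

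The first route costs one call per affected child and a short SAP addition. The second costs a wording change, alignment of the withdrawal contact, one extra summary and a shorter stated safety follow-up. The length of follow-up is for the sponsor to decide.

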6.1.5.3. Analysis of adverse events

Adverse events will be coded according to the Medical Dictionary for Regulatory Activity (MedDRA current version).

Adverse events will be individually listed per subject number, presenting System Organ Class

(SOC), preferred term, emergence, description, date and time of onset, date and time of last study drug administration before adverse event, duration, time from onset since last study drug administration, frequency, severity and seriousness, relationship to study drug, the required action taken (corrective treatment, hospitalization....) required, and outcome if any.

It consists in the evaluation of the number of adverse events and in the number of subjects reporting these adverse events.

• Treatment Emergent Adverse Events (TEAE)

Adverse events will be classified into pre-defined standard categories according to chronological criteria:

- Treatment Emergent AEs (TEAE): AEs that occurred for the first time, or if present before that worsened during the exposure to the study drug(s).
- Non-Treatment Emergent AEs (NTEAE): AEs that occurred before the study drug administration.

• Assessment of Intensity

An assessment of the relative intensity of an adverse experience is based on the investigator's clinical judgment by using the following scale. The **maximum** intensity encountered during the evaluation period should be checked.

The assessment of intensity should be independent of the assessment of the seriousness of the AE.

- **Mild:** No significant interference with the subject's usual activities: acceptable, disappeared without residual effect
- Moderate: moderate interference with study the subject's usual activities.
- **Severe:** major interference with study the subject's usual activities, considered as unacceptable by the physician or required specific treatment or required discontinuation from the study.

• Assessment of Causality

The investigator will make judgment considering whether or not, in his opinion, the AEs are related to the study drug according to the following causal relationship assessment of suspected adverse reactions:

• **Related / likely:** Clearly related to the investigational agent / procedure, i.e. an event that follows a reasonable temporal sequence from administration of the

BIOPROJET Protocol P11-06/ BF2.649 EudraCT number: 2013-001506-29

study intervention, follows a known or expected response pattern to the suspected intervention, that is can be confirmed by improvement on stopping and reappearance of the event after rechallenge and that could not be reasonably explained by the known characteristics of the subject's clinical state.

- **Possibly related** / **Possible:** Follows a reasonable temporal sequence from administration of the study intervention, follows a known or expected response pattern to the suspected intervention, but that could readily have been produced by a number of other factors.
- **Not related** / **Unlikely:** Clearly and incontrovertibly due only to extraneous causes, and does not meet criteria listed under possible (possibly related) or likely (related).

AE outcome

All adverse Event outcomes should be documented at the last visit at the latest according to the following criteria:

- Ongoing *
- Resolved
- Unknown
- Recovered with sequelae **
- Recovered without sequelae
- Death related to adverse reaction
- Death not related to adverse reaction
- * If an adverse event is still *ongoing* at the last visit the patient must be follow-up until the outcome can be documented without using the "ongoing" assessment.
- ** A description of sequelae must be provided in the CRF

6.1.5.4. Reporting Serious Adverse Event or Serious Adverse Drug Reaction

All serious adverse events (SAE) or Serious Adverse Drug Reaction (SADR), whatever the dose, the therapeutic or diagnostic reason, have to be reported **immediately (within 24 hours)**, by any means to the Sponsor's defined representative:

Pharmacovigilance Responsable contact:

⊠ Bioprojet [name]

BIOPROJET Protocol P11-06/ BF2.649 EudraCT number: 2013-001506-29 Version 3.0 September 30th, 2020

The investigator must inform the site monitor.

In case of SAE the investigator must complete the specific form "Serious Adverse Event" and

send it within 48 hours to Bioprojet and the duplicated SAE form dully completed and signed

to the monitor. After the initial report, the SAE should be promptly followed by a detailed

writing report including all data allowing to document the event and notably the anonymous

copies (subject identification code: treatment number and initials) from hospitalization's report

and additional performed examination(s). The list of the pertinent documents deemed necessary

to assess the gravity and the potential relationship is given at the end of the case report form.

The investigator should also report to the monitor all elements concerning the follow-up of the

serious adverse event.

For reported death, the investigators should supply the Sponsor and the IRB/IEC with any

additional requested information such as autopsy reports if available and terminal medical

reports.

The "Serious Adverse Event" form and the instructions on completion are provided in the

investigator's study file. The "Instructions for Completing the SAE Form" give more detailed

guidance on the reporting of serious adverse events, significant overdose cases, and Adverse

Events initially reported as non serious that become serious.

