An Adverse Reaction, the nature or severity of which is not consistent with the applicable

BIOPROJET Version 3.0
Protocol P11-06/ BF2.649 September 30th, 2020

EudraCT number: 2013-001506-29

product information (e.g. Investigator Brochure).

• Serious Adverse Event (SAE) or Serious Adverse Drug Reaction (Serious ADR)

A Serious Adverse Event is one that at any dose:

- Results in death;
- Is life-threatening¹;
- Requires patient hospitalization or prolongation of existing hospitalization;
- Results in persistent or significant disability/incapacity²;
- Is a congenital anomaly/birth defect;
- Is medically important³.

1 "Life-threatening" means that the patient was at immediate risk of death at the time of the serious adverse event; it does not refer to a serious adverse event that hypothetically might have caused death if it were more severe.

2 "Persistent or significant disability or incapacity" means that there is a substantial disruption of a person's ability to carry out normal life functions.

³ Medical and scientific judgment should be exercised in deciding whether other adverse events may be considered serious because they jeopardize the patient, or may require intervention to prevent one of the other outcomes listed in the definition above. The List of Critical Terms (1998 adaptation of WHO Adverse Reaction Terminology Critical Terms List) should be used as guidance for adverse events that may be considered serious because they are medically important.

Cases involving cancer as an Adverse Event should be reported as "serious" using the criterion "medically important" if no other serious criterion is met.

Cases of overdose with an adverse event that meets one of the criteria given above should of course be reported as "serious". There is no antidote; in case of overdose, the patient has to be hospitalized in order to control his/her vital functions.

A serious adverse drug reaction is a serious adverse event which is related to the medicinal product whatever the dose.

• Clarification of the difference in meaning between "severe" and "serious"

The terms "severe" and "serious" are not synonymous:

- "severe" is used to **describe the intensity** (severity) of a specific event, which could be rated *mild*, *moderate or severe*. The event itself, however, may be of relatively

minor medical significance (such as severe headache).

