## 4.5.4.1 Adverse events

The Adverse events (AEs) were reported with the following information: Description, Visit number when AE was reported, Dose of study drug when AE occurred (10 mg, 20 mg, 40 mg, NA), Date of onset or worsening and end date or ongoing, Intensity (mild, moderate, severe), Frequency (once, intermittent and number and period, continuous, unknown), Action taken with studied drug (none, dose modification, temporary interruption, discontinued), Action taken with event (none, corrective treatment, additional exploration, hospitalization  $\leq$  24 hr, hospitalization > 24 hr), Serious adverse event (SAE) (yes, no), Outcome (recovered, recovered with sequelae, worsened, not yet recovered, death), Imputability (likely related, possibly related, unlikely related), Etiology (studied drug, concomitant treatment, associated disease, other, unknown)

Number of events, number and percentage of patients reporting at least one event, presented by primary system organ class (SOC) and preferred term (PT), over the period V2-V8, will be provided for:

- AE
- Serious AE,

- Treatment emergent AE (TEAE), Treatment emergent AE (TEAE) during the stable dose period, TEAE leading to IMP withdrawal, TEAE related to IMP, serious TEAE, severe TEAE, non-serious TEAE (EUDRACT), Treatment emergent fatal AE.
- Special Interest TEAE (SITEAE).

TEAE also will be described according to the intensity, dose in the stable dose period and outcome.

In case a same patient presented the same AE (i.e. same AE as defined according to SOC and PT) several times during the study, only one occurrence per patient will be reported, but the total number of events will be given.

In addition, only TEAEs with incidence >5% (i.e. % of patients with >5 % for a given PT in at least one treatment group) will be presented by SOC and PT in the SAF population.

A listing with all the individual AEs with the associated information will be provided.

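### The causality scale has no class for a plausibly timed event of a kind not already known for pitolisant, although the protocol's own definition calls it an adverse drug reaction

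*Protocol*

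**What the plan says.** Protocol 6.1.5.3 (Assessment of Causality) asks the investigator to judge each event on a three-class scale.

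- *Related / likely* needs reasonable timing and, among other conditions, a recognised pattern: "study intervention, follows a known or expected response pattern to the suspected intervention, that is can be confirmed by improvement on stopping".
- *Possibly related / Possible* also needs reasonable timing, and that the event "follows a known or expected response pattern to the suspected intervention, but that could readily have been produced by a number of other factors".
- The remaining class, *Not related / Unlikely*, is reserved for an event that is "Clearly and incontrovertibly due only to extraneous causes, and does not meet criteria listed under possible" or likely.

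Protocol 6.1.5.1 sets a different threshold. An adverse drug reaction is a response for which causality is at least a reasonable "possibility, i.e. the relationship cannot be ruled out". That paragraph sends the reader to §7.2.5.3 for the causality assessment, but the scale is in 6.1.5.3. The same section defines an unexpected adverse drug reaction as "An Adverse Reaction, the nature or severity of which is not consistent with the applicable" product information.

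SAP 4.5.4.1 lists the collected field as "Imputability (likely related, possibly related, unlikely related", with no option for an event that cannot be assessed, and next to it an Etiology field (studied drug, concomitant treatment, associated disease, other, unknown). SAP 4.1.5.6 counts a treatment-emergent event as related if it is rated likely or possible, or if the rating is missing. SAP 4.5.4.1 plans a table of such events.

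**The concern.** A definition and the scale that is meant to apply it should select the same events. Here the definition asks whether a relationship can be ruled out, while both positive classes of the scale also ask whether the event resembles something already known or expected. Prior knowledge of an effect thus becomes a condition for attributing an event to the drug.

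This is awkward in a trial whose main objectives (Synopsis) include safety in children and adolescents, long-term safety and drug-drug interactions. Each of these can bring up effects not described before. At stake are the content of the related-events table and consistency between centres, since sites that meet an event with no matching class may resolve it differently.

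**Working it through.** No arithmetic applies: the point depends on no rate, sample size or error level, and the plan gives no figure to reproduce. The check is to run test events through the written criteria.

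**Event A.** It starts after dosing with plausible timing, has no clear other cause, and is of a kind not previously known for pitolisant.

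| Rule | Deciding condition | Event A |
|---|---|---|
| Related / likely (Protocol 6.1.5.3) | known or expected pattern | not met |
| Possibly related (Protocol 6.1.5.3) | known or expected pattern | not met |
| Not related / Unlikely (Protocol 6.1.5.3) | certainly and only extraneous | not met |
| Adverse drug reaction (Protocol 6.1.5.1) | relationship cannot be ruled out | met |
| Unexpected adverse drug reaction (Protocol 6.1.5.1) | a reaction whose nature is not in the product information | met |

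Event A is a reaction by definition, yet it has no place on the scale to which that definition refers.

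What follows depends on what the site enters, under the related rule in SAP 4.1.5.6:

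| Entry | Counted as related? | Agrees with the 6.1.5.3 criteria? |
|---|---|---|
| likely or possibly related | yes | no, pattern condition not met |
| unlikely related | no | no, cause not certainly extraneous |
| blank | yes | no class applied |

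No entry applies the criteria as written. Only 'unlikely' removes the event from the related table. That choice is easy to make, because the label is milder than the definition behind it.

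**Event B.** This is a known effect at a severity not described in the product information. Timing and pattern are both satisfied, so it can be rated possible or likely, and it is still unexpected under 6.1.5.1 because of its severity. The gap therefore concerns reactions that are new in nature, not all unexpected reactions.

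**The case against.** The strongest reply is that little depends on this scale, and much of that reply stands.

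- The trial is randomised and placebo-controlled. Protocol 3.7.2.3 makes treatment-emergent events the main safety parameters, and SAP 4.5.4.1 tabulates all, serious, severe, fatal and withdrawal-leading treatment-emergent events without regard to causality. A new effect can show up as a difference between arms however it was coded.
- Protocol 6.1.5.4 sends every serious event to the sponsor within 24 hours with no causality filter, followed by documents for assessing the relationship. The instructions for the serious-event form are in the investigator's file and are not part of the documents under review.
- The Etiology field lets an investigator name the study drug whatever the causality rating, and the individual listing carries that information. It does not, however, feed the related rule in SAP 4.1.5.6.
- Causality is the investigator's opinion, and 'response pattern' might be read broadly as pharmacologically plausible. The protocol does not give that reading, and leaving it to each site invites inconsistent coding.

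Three stronger conclusions are tempting, and the documents do not support them. A reader might infer that investigators are forced to enter 'unlikely'; the criteria for that class also fail, so the result is a gap. A reader might infer that no unexpected reaction can be coded as related; event B shows otherwise. A reader might infer that a serious unexpected reaction would go unrecognised; serious events reach the sponsor regardless of coding, and the documents do not show what causality review the sponsor then makes.

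**Conclusion.** The point holds as an internal conflict. Protocol 6.1.5.3 cannot classify an event that Protocol 6.1.5.1 defines as an adverse drug reaction and refers to that scale, and the reference carries the wrong section number. The conclusion assumes that the pattern condition is applied as written.

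The practical effect is limited to relatedness coding and the planned related-events table. That table loses an event only where a site enters 'unlikely'. Overall safety tabulation and serious-event reporting are untouched. The documents give no incidence for previously unknown reactions and no indication of how sites resolve the gap, so any count of affected events would be a guess. It is worth correcting because the written rule contradicts the protocol's own definition and the repair is small.

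**What to change.** - In Protocol 6.1.5.3 and the matching CRF guidance, remove the response-pattern condition from *Possibly related*. Define that class as a reasonable temporal sequence in which a causal relationship cannot be ruled out, as in 6.1.5.1. Keep the pattern criterion for *Related / likely* only.
- In Protocol 6.1.5.1, change the cross-reference from §7.2.5.3 to 6.1.5.3.
- Before database lock, and blind to treatment, query events coded 'unlikely' whose Etiology entry is 'studied drug' or 'unknown'. Both fields are already collected, and the blind review meeting in SAP 4.4 is a natural place for it.

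The related rule in SAP 4.1.5.6 needs no change, since it already counts possible events. The cost is one reworded definition, one corrected reference and a short query round. The number of related treatment-emergent events may rise slightly.
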